## 6.2.3. Clinical laboratory sampling

Non-fasting samples for clinical laboratory analysis will be collected by a qualified staff member at Visit 1, at Visit 2 prior to randomization and at Visit 8. The following tests, at a minimum, will be conducted:

| Chemistry Panel                  | Complete Blood Count          |
|----------------------------------|-------------------------------|
| Albumin                          | Hematocrit                    |
| Alkaline phosphatase             | Hemoglobin                    |
| Alanine aminotransferase (ALT)   | Platelet count                |
| Aspartate aminotransferase (AST) | Red blood cell morphology     |
| Blood urea nitrogen (BUN)        | Red blood cell count          |
| Bicarbonate                      | White blood cell count        |
| Calcium                          | White blood cell differential |
| Chloride                         | % & absolute                  |
| Creatinine                       | Basophils                     |
| Glucose                          | Eosinophils                   |
| Lactate dehydrogenase (LDH)      | Lymphocytes                   |
| Phosphorus                       | Monocytes                     |
| Potassium                        | Neutrophils                   |
| Sodium                           |                               |
| Total bilirubin                  |                               |
| Total protein                    |                               |
| Uric acid                        |                               |

The results of the clinical laboratory tests will be reported on the laboratory's standard reports. The investigator must note NCR or CR to define the clinical relevance of any result that is outside the normal range for the laboratory. The investigator must date and initial every laboratory report.

The investigator must review the Visit 1 laboratory results for each subject prior to Visit 2. The subject must not be randomized at Visit 2 if any of the Visit 1 results are outside normal range for the laboratory AND, in the opinion of the investigator, CR.

The investigator must report all laboratory results that are BOTH outside the normal range for the laboratory AND, in the opinion of the investigator, CR as medical history if found prior to the first study medication application or as an AE if found after the first study medication application begins (Section 7.1). The investigator must review all laboratory reports in a timely manner

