# 5. INVESTIGATIONAL PLAN

## 5.1. Study Design

This is a randomized, double-blind, vehicle-controlled, parallel group study of 2 concentrations of A-101 Solution (*i.e.*, 40% and 32.5%) and its matching A-101 Solution Vehicle in subjects with SK. Eligible subjects will have 1 appropriate SK target lesion on the face.

The study will be conducted at multiple US study centers. The study visit schedule is:

- Visit 1 (Day -13 to 0) enrollment; start screening period
- Visit 2 (Day 1) randomization; study medication application
- Visit 3 (Day 8) no treatment follow-up
- Visit 4 (Day 22) follow-up visit where target lesions that meet the retreatment criteria will receive a second study medication application
- Visit 5 (Day 29) no treatment follow-up
- Visit 6 (Day 50) no treatment follow-up
- Visit 7 (Day 78) no treatment follow-up
- Visit 8 (Day 106) no treatment follow-up; end of study.

At Visit 1, the investigator will identify 1 SK target lesion on the face for treatment for each subject. Subjects may have more than 1 SK lesion, but only the target lesion will be evaluated and treated. The investigator will also collect blood samples for clinical laboratory safety tests to determine the subject's eligibility for randomization.

At Visit 2, the investigator will randomize eligible subjects and perform an initial study medication application.

At Visit 3, subjects will be seen for a no treatment follow-up.

At Visit 4, subjects will be seen for follow-up and any target lesion that meets the retreatment criteria (*e.g.*, PLA >0) will receive a retreatment study medication application.

At Visits 5 through 7, subjects will be seen for a no treatment follow-up.

At Visit 8, subjects will be seen for a no treatment follow-up and be discharged from the study.

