| Study medication application                            |          | Х                     |   | X         |    |    |    |     | 5.7.6    |
| Subject instructions                                    | Х        | Х                     | Х | Х                     | Х  | Х  | Х  | Х   | 5.6      |
| Concomitant therapies                                   | Х        | Х                     | Х | Х                     | Х  | Х  | Х  | Х   | 4.5.2    |
| Adverse events  | Х        | Х                     | X | X                     | Х  | Х  | Х  | Х   | 7        |

 Performed prior to the study medication application

Performed prior to and after the study medication application

Only for Target Lesions that meet the retreatment criteria.

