#### 7.1. Definitions

#### 7.1.1. Adverse events (AE)

An AE is any untoward medical occurrence in a patient or clinical investigation subject administered a study medication(s) and which does not necessarily have a causal relationship with the study medication. An AE can therefore be any unfavorable and unintended sign or symptom associated with the use of a study medication (including an abnormal laboratory finding), whether or not related to the study medication.

Thus any new, clinically relevant worsening of an existing sign, symptom or disease, should be considered an AE.

Worsening of any of the target lesion assessments should be reported as an AE ONLY if the use of the study medication is interrupted or discontinued or if therapy is required to manage the event.

The investigator must, for any AE associated with a target lesion, question the subject in detail to determine if there are any confounding factors (*e.g.*, irritation by clothing or activity, sunburn) for any such AE.

Report any event that requires use of the eyewash kit [Section 5.7.6] as an AE for "eye irritation". For all AEs of this type:

- Contact the medical monitor (see contact information on Page 1, or in Section 7.2.2) immediately (within 24 hours)
- Unblind the study medication for the subject (Section 5.10.2)
- Arrange for the subject to be transported to the most appropriate hospital emergency room (ER) and provide the study medication identification information to the appropriate ER staff
- Follow the course of the AE
- Report the event as an SAE if appropriate (Section 7.1.2).

Every new episode or clinically relevant worsening of a chronic condition (*e.g.*, headaches, seasonal allergies, depression, and hypertension) should be reported as a separate AE, even if the condition is reported in the subject's medical history.

The investigator should, when certain, report a diagnosis rather than the signs, symptoms or clinically relevant abnormal laboratory values associated with the AE. Otherwise, signs, symptoms or abnormal laboratory values may be used to describe the AE.

Any CR abnormality discovered prior to the first study medication application should be reported as medical history, not as an AE.

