### 9.2. Statistical Analysis of Safety Data

Descriptive statistics will be calculated on the safety parameters using the ITT population. The proportion of subjects with treatment-emergent adverse events will be tabulated and presented by treatment and Medical Dictionary for Regulatory Activities (MedDRA) System Organ Class. Vital signs, LSR scores and clinically relevant abnormal laboratory results will also be tabulated and presented by study medication. No inferential testing will be performed.

Data from all randomized subjects will be presented and summarized. Safety summaries by study medication group will include listings by study medication of adverse events incidences within each MedDRA System Organ Class, and changes from pre-application values in vital signs. Adverse event summaries will be presented by study medication showing the proportion of subjects experiencing adverse events, both overall and by MedDRA System Organ Class.

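### A clinically relevant abnormality in the pre-dose Visit 2 blood sample can be reported as an adverse event, because the rule goes by when it is found and not by when the sample was drawn.

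*Combined protocol and SAP*

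**What the plan says.** Section 6.2.3 has laboratory samples taken "at Visit 1, at Visit 2 prior to randomization and at Visit 8". In the flow chart (Section 5.2) the Visit 2 sample carries the footnote "Performed prior to the study medication application". The first application falls on the same day; the schedule in Section 5.1 reads "Visit 2 (Day 1) randomization; study medication application".

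The reporting rule in Section 6.2.3 applies to results that are both outside the laboratory's normal range and, in the investigator's opinion, clinically relevant (CR). Its history half reads "CR as medical history if found prior to the first study medication application", and its AE half continues "or as an AE if found after the first study medication application begins". Section 7.1.1 states the history half again for CR abnormalities in general: "Any CR abnormality discovered prior to the first study medication application should be reported as medical history, not as an AE".

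For the analysis, Section 9.2 says: "The proportion of subjects with treatment-emergent adverse events will be tabulated". Its second paragraph also summarises, by study medication, the share of subjects with adverse events, this time without the treatment-emergent qualifier.

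**The concern.** Whether a laboratory abnormality was present before treatment depends on when the blood was drawn. The protocol classifies it by when somebody learns of it. For the Visit 2 sample the two dates can fall on opposite sides of the first application.

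A CR abnormality in blood drawn before any study medication cannot have been caused by it. If its result is read after dosing, the protocol still requires it to be reported as an AE. Safety is a stated objective (Section 3) and Section 9.2 plans no inferential testing, so the descriptive AE proportions are the safety result. Random allocation spreads such cases over the arms on average, but it does not correct the absolute rate within an arm.

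**Working it through.** The plan gives no figure on this point, so there is none to reproduce. The check compares the visit sequence with the reporting rule, followed by a calculation for scale.

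**Sequence**

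1. The Visit 2 sample precedes randomization (Sections 5.2, 5.3.2 and 6.2.3). The first application follows at the same visit.
2. Before Visit 2 the investigator must have reviewed the Visit 1 results (Sections 5.3.2 and 6.2.3). Section 5.3.2 lists 17 steps before randomization. They include the blood draw but no review of its result.
3. Section 5.9 lists supplies for shipping samples and reporting results. No turnaround time is given. That the Visit 2 result arrives after dosing is an inference, but the likely one.
4. The rule in Section 6.2.3 turns on when the result is found, and Section 7.1.1 on when the abnormality is discovered. Neither refers to the collection date. A CR result from step 1 that is read after the application has begun therefore falls in the AE half.
5. A subject with a CR Visit 1 result must not be randomized (Section 6.2.3). Among randomized subjects, Visit 2 is thus the only scheduled draw that can yield a pre-dose CR result. If its results return after dosing, the history half has almost nothing left to apply to in the laboratory data.
6. Section 7.1.4 starts non-serious AE reporting at the first application but does not say how a laboratory finding is dated. Section 9.2 uses treatment-emergent without defining it.

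**Scale**

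Inputs: N = 108 randomized, about 36 per group (Section 4.1). Let p be the proportion of randomized subjects with a new CR abnormality in the Visit 2 sample whose result is found after dosing. The documents give no value for p; the range below is an assumption.

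Expected cases = N × p. Chance of at least one in the trial = 1 − (1 − p)^108.

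| Assumed p | Cases in trial (108 × p) | Cases per arm (36 × p) | Chance of at least one in trial |
|---|---|---|---|
| 0.5% | 0.54 | 0.18 | 42% |
| 1% | 1.08 | 0.36 | 66% |
| 2% | 2.16 | 0.72 | 89% |
| 3% | 3.24 | 1.08 | 96% |

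One misclassified subject in an arm of 36 adds 1/36 = 2.8 percentage points to that arm's AE proportion. If results were classified by collection date, the expected number would be 0 at every p.

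**The case against.** The strongest case against is that the rule governs what a site reports, while the first table in Section 9.2 is limited to treatment-emergent events. In its ordinary sense that term would leave out a finding dated to a pre-dose sample. Section 7.1.1 also describes an AE as arising in a subject who has been given study medication, and Section 7.1.6 lets the investigator weigh timing, so such a finding would naturally be judged not related. The rule in Section 5.7.6 for ending retreatment counts only discontinuations for related AEs and should not be touched. Visit 1 screening, the good-health criterion and the short interval to Visit 2 keep the number low, and p could lie below the range shown.

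Much of this stands as a limit on size. It does not remove the problem. The term is undefined, the second AE summary in Section 9.2 lacks the qualifier, and a verdict of not related does not take an event out of an AE count. If some investigators read found as meaning present in the sample, sites may classify the same result differently, which is also a reason to clarify.

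A reader might go further than the documents allow in three ways:

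- That every abnormal Visit 2 result becomes an AE. Section 6.2.3 covers only out-of-range results judged CR.
- That such findings are certain to be counted as treatment-emergent. With the term undefined, they could be; the text does not settle it.
- That the trial's laboratory baseline is thereby labelled an event. No section names Visit 2 as the laboratory baseline; Section 9.2 plans changes from pre-application values for vital signs only.

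**Conclusion.** The point holds in a limited form. Followed literally, Sections 6.2.3 and 7.1.1 report a new CR abnormality in the pre-dose Visit 2 sample as an AE whenever its result is found after the application has begun, and Section 9.2 has no stated rule to keep it out of the summaries.

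The size is likely small: about 0.5 to 3.2 cases in the whole trial, or roughly 0.2 to 1.1 per arm. This rests on two assumptions: a rate of 0.5% to 3%, for which the documents offer no source, and the return of Visit 2 results after dosing, which is inferred from shipping. It would be too strong to expect one or two false events in every arm, since most of the assumed range gives fewer than one per arm. No efficacy analysis is affected, and no between-arm bias is expected on average. The correction is worth making because the rule misclassifies by construction and costs little to change.

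**What to change.** - **Sections 6.2.3 and 7.1.1:** classify a CR abnormality by the time the sample was collected or the measurement taken, relative to the start of the first application, whatever the date the result was received or reviewed. CR findings from the pre-application Visit 2 sample then go to medical history, and those from later samples are AEs.
- **Section 6.2.2:** make the same change for vital signs, which use the same wording. Vital signs are known when measured, so this is for consistency; it avoids leaving two different rules in the protocol.
- **Section 9.2:** define treatment-emergent to match, using collection or measurement time for laboratory and vital-sign findings, and state whether the second AE summary uses the same definition.
- **Section 7.1.4:** leave SAE reporting from signature of the consent form as it is, and say that the history rule does not override it.

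The cost is a wording change and matching CRF instructions. No extra samples, visits or data are needed.

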## 6.2.4. Urine pregnancy tests

The investigator or designee will perform a urine pregnancy test for subjects who are WOCBP (Section 6.2.4) at Visit 1, at Visit 2 prior to randomization and at Visit 8. The urine pregnancy test kits used must have a minimum sensitivity of 25-mIU ß-HCG/milliliter (mL) of urine.

Subjects who are WOCBP must have a negative pregnancy test result at Visit 1 to continue in the study and at Visit 2 to be randomized.

If the result of any post-randomization urine pregnancy test is positive, the subject will be withdrawn from the study and the subject's pregnancy documented and followed (Section 8).

#### 6.3. Other Evaluations

#### 6.3.1. Demographics and medical history

At Visit 1, the investigator or designee will interview each subject to obtain demographic information including date of birth, sex at birth, Fitzpatrick skin type, race and, if appropriate, ethnicity.

At Visit 1, the investigator must determine each subject's Fitzpatrick skin type.

The investigator or designee will interview each subject to obtain medical history information related to all medical conditions and disease states that, at Visit 1:

- Are ongoing
- Require concomitant therapy
- Are, in the opinion of the investigator, relevant to the subject's study participation.

## 6.3.2. Standardized photography

At Visits 1, 2, 4 and 8 an investigational center staff member other than the investigator, at one selected center ONLY, will take standardized color photographs of the target lesion.

Target lesion photographs will be digitally modified prior to any publication to ensure the subject's identity is not revealed.

The photographs are to document the appearance of the subjects' target lesion.

At study visits where a study medication application is performed (*i.e.*, Visit 2 and potentially Visit 4) the photographs must be taken prior to the study medication application.

Care must be taken to ensure the same lighting, background, subject positioning relative to the camera and camera settings are used for each photograph.

Equipment, supplies, training and detailed instructions for obtaining and managing the photographs will be provided to the investigational center prior to the initiation of subject enrollment.

## 7. ADVERSE EVENTS

Adverse events will be monitored throughout the study and immediately reported on the appropriate Aclaris Therapeutics, Inc. AE CRF.

#### 7.1. Definitions

#### 7.1.1. Adverse events (AE)

An AE is any untoward medical occurrence in a patient or clinical investigation subject administered a study medication(s) and which does not necessarily have a causal relationship with the study medication. An AE can therefore be any unfavorable and unintended sign or symptom associated with the use of a study medication (including an abnormal laboratory finding), whether or not related to the study medication.

Thus any new, clinically relevant worsening of an existing sign, symptom or disease, should be considered an AE.

Worsening of any of the target lesion assessments should be reported as an AE ONLY if the use of the study medication is interrupted or discontinued or if therapy is required to manage the event.

The investigator must, for any AE associated with a target lesion, question the subject in detail to determine if there are any confounding factors (*e.g.*, irritation by clothing or activity, sunburn) for any such AE.

Report any event that requires use of the eyewash kit [Section 5.7.6] as an AE for "eye irritation". For all AEs of this type:

- Contact the medical monitor (see contact information on Page 1, or in Section 7.2.2) immediately (within 24 hours)
- Unblind the study medication for the subject (Section 5.10.2)
- Arrange for the subject to be transported to the most appropriate hospital emergency room (ER) and provide the study medication identification information to the appropriate ER staff
- Follow the course of the AE
- Report the event as an SAE if appropriate (Section 7.1.2).

Every new episode or clinically relevant worsening of a chronic condition (*e.g.*, headaches, seasonal allergies, depression, and hypertension) should be reported as a separate AE, even if the condition is reported in the subject's medical history.

The investigator should, when certain, report a diagnosis rather than the signs, symptoms or clinically relevant abnormal laboratory values associated with the AE. Otherwise, signs, symptoms or abnormal laboratory values may be used to describe the AE.

Any CR abnormality discovered prior to the first study medication application should be reported as medical history, not as an AE.

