#### **Evaluations – Safety:**

The investigator and subject, as indicated, will evaluate Local Skin Reactions (LSR) for the target lesion. In addition, clinical laboratory safety tests, vital sign readings, concomitant therapies, urine pregnancy tests and adverse events (AEs) information will be assessed throughout the study.

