Numerous treatment options exist, and include a plethora of destructive/ablative modalities such as liquid nitrogen cryotherapy, electrodesiccation, lasers of various wavelengths (ablative and non-ablative), radio-frequency ablation, and surgical removal by curettage or surgical excision. There is, however, a notable lack of wellcontrolled clinical trials comparing the efficacy, complications and complication rates of these treatments. There is great variability among practitioners in the methods employed using each of these techniques (e.g., variability in contact time and method of freezing the lesions with liquid nitrogen) with great variability of the results. None of these treatments is, in fact, approved by the Food and Drug Administration (FDA) for the treatment of seborrheic keratosis. While these methods can be effective, many require specialized training and/or the use of expensive equipment, they are painful and may require anesthesia and/or analgesia, and they are often complicated by significant adverse outcomes. Both hypopigmentation and hyperpigmentation, which may be transient, but are often permanent, are common, as is scarring at the treatment site, and the typical post-surgical risks of bleeding and infection increase the risk that the result of the treatment of these lesions may be worse than the disease itself.

Hydrogen peroxide (H2O2) is a compound that is ubiquitous in the environment. It is the simplest peroxide and a potent oxidizing agent commonly used in innumerable household goods including chlorine-free bleaches, general-purpose cleaning products, and disinfectants. Additionally, H2O2 has been employed as the oxidizing component in hair dyes, and has been used in oral hygiene products and tooth-whitening systems for many years. In industry, it is employed in the treatment of wastewater. In high concentrations, it is used in bleaching paper, pulp, and textiles. Clinically, in addition to its use as an oral topical agent noted above, H2O2 is widely employed at low concentrations (*e.g.*, 3%-6%) as a wound irrigant and topical antiseptic/disinfectant, and has been in use medicinally since its introduction into clinical practice by Richardson in 1858.

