# 5.3.7. Visit 8 (Day 106)

This visit must occur 105 days (±4 days) after Visit 2.

At this visit, the investigator or designee will perform the following procedures:

- 1. Query the subject in a non-directive manner about any changes in her/his health since the previous visit and report all AEs on the appropriate form (Section 7.2.1)
- 2. Query the subject about any changes in her/his concomitant therapies since the previous visit and report changes on the appropriate form (Section 4.5.2)
- 3. Confirm the subject continues to comply with all study restrictions and has followed all study instructions (Section 5.5)
- 4. Measure vital signs (Section 6.2.2)
- 5. Collect blood samples for clinical laboratory tests (Section 6.2.3)
- 6. Perform a urine pregnancy test for WOCBP (Section 6.2.4)
- 7. Confirm the location of the target lesion (Section 5.4)
- 8. AT ONE SELECTED CENTER ONLY take standardized color photographs of the target lesion (Section 6.3.2)
- 9. Have the subject perform an SSA for the target lesion (Section 6.1.1)
- 10. Have the subject perform a Local Skin Reaction assessment of the symptoms for the target lesion (Section 6.2.1)
- 11. ONLY AFTER THE SUBJECT COMPLETES THE SSA perform PLA for the target lesion (Section 6.1.2)
- 12. Perform a Local Skin Reaction assessment of the signs for the target lesion (Section 6.2.1)
- 13. Measure the dimensions of the target lesion (Section 6.1.3)
- 14. Discharge the subject from the study.

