## 6.2.1. Local Skin Reactions (LSR)

The LSR assessment is the investigator's assessment of the signs and the subject's assessment of the symptoms associated with irritation at the target lesion site (*i.e.*, the target lesion and the skin immediately surrounding the target lesion exposed to study medication). The investigator and subject must NOT refer to any other evaluation to assist with these assessments. This is not a comparison with the assessment at any other time point.

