## 7.2. **Reporting Procedures**

## 7.2.1. Procedures for reporting adverse events

At each post enrollment visit, the investigator will question the subject to elicit AEs using a non-directive question such as "Has there been any change in your health since the previous study visit?"

The investigator/designee will monitor the subject for at least 20 minutes after the Application Completion Time at Visit 2 and at Visit 4 to elicit AEs in a similar manner.

If appropriate, based on the subject's response to non-directed questioning regarding AEs, the investigator will follow-up with directed questions and appropriate evaluations.

Any AE noted during the reporting period (Section 7.1.4) must be reported in the source documents and on the appropriate AE CRF.

AEs that are defined as "Not Related" to the study medications will be followed until they are resolved or until the subject's last study visit. AEs that are defined as "Related" to the study medications will be followed until they are resolved or, if not resolved after the subject's last study visit, until in the opinion of the investigator, the AE reaches a clinically stable outcome with or without sequelae.

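### Section 7.1.1 can keep untreated, non-serious scarring, atrophy, ulceration or pigment change after the last application out of the AE counts, leaving it without follow-up after Visit 8

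*Combined protocol and SAP*

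**What the plan says.** Section 7.1.1 gives two instructions in succession. The general one is inclusive: "Thus any new, clinically relevant worsening of an existing sign, symptom or disease, should be considered an AE". The next one narrows this for the lesion under study: "Worsening of any of the target lesion assessments should be reported as an AE ONLY if the use of the study medication is interrupted". Discontinuation and a need for therapy are the other qualifying conditions. The protocol does not define which assessments the restriction covers.

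Section 6.2.1 lists eleven LSR signs graded 0 to 3 by the investigator. Five are ulceration, post-inflammatory hyper-pigmentation, post-inflammatory hypo-pigmentation, atrophy and scarring. All eleven are graded at Visits 3 and 5 to 8, and before any application at Visits 2 and 4.

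Sections 5.7.1 and 5.7.6 allow at most two applications, at Visit 2 and, if the retreatment criteria are met, at Visit 4.

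Section 7.2.1 follows related AEs to resolution or, past the last visit, "until in the opinion of the investigator, the AE reaches a clinically stable outcome with or without sequelae". Unrelated AEs are followed no later than the last visit. Section 7.2.2 has a similar rule for SAEs. The last step of Visit 8 (Section 5.3.7) is "Discharge the subject from the study".

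Section 9.2 tabulates treatment-emergent AEs by treatment and System Organ Class, and LSR scores separately by study medication.

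**The concern.** The restriction has two triggers: a change in the use of study medication, or a need for therapy. With at most two in-clinic applications, the first trigger disappears after Visit 4. A scar, an atrophic patch or a change in pigment may need no therapy, so neither trigger is met however marked the sign is.

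These are the harms the protocol itself holds against existing treatments. Section 2.1 says of them: "Both hypopigmentation and hyperpigmentation, which may be transient, but are often permanent, are common, as is scarring at the treatment site". It then says proof-of-concept data suggest that A-101 has the potential to resolve lesions with minimal risk of these outcomes. Section 3 makes safety on the face an objective. An AE table could show none of these events while the LSR table shows them, and a subject could be discharged with a residual facial sign whose outcome is never recorded.

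**Working it through.** **1. The untreated period.** The Synopsis and Section 5.6 state an 84-day no-treatment follow-up. From the visit days: Day 106 − Day 22 = 84 days, which reproduces it. Visit 4 falls 21 ± 4 days and Visit 8 falls 105 ± 4 days after Visit 2, so the range is:

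- shortest: (105 − 4) − (21 + 4) = 101 − 25 = 76 days
- longest: (105 + 4) − (21 − 4) = 109 − 17 = 92 days

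A subject who is not retreated has 105 days (101 to 109) from the only application to Visit 8. Until Visit 4 a second application is still possible, and withholding it because of a reaction could be taken as an interruption. The gap is therefore clear only after Visit 4.

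**2. Which triggers remain.** After Visit 4 no subject in any group has an application pending, so medication cannot be interrupted or discontinued. Only the need for therapy remains. LSRs are graded four more times: Visits 5, 6, 7 and 8 (Days 29, 50, 78 and 106).

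**3. Does the restriction reach LSRs?** The passages point both ways.

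- *For inclusion:* the Synopsis says the investigator and subject "will evaluate Local Skin Reactions (LSR) for the target lesion", and the visit procedures in Sections 5.3.2 to 5.3.7 repeatedly call for LSR assessments of the target lesion.
- *Against:* Section 6.1 places SSA, PLA and dimensions under effectiveness, while Section 6.2.1, under safety, defines the LSR site as "the target lesion and the skin immediately surrounding the target lesion exposed to study medication", which is wider than the lesion.

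**4. Consequence under each reading**, for a new, non-serious, untreated scar seen at Visit 6 and still present at Visit 8:

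| Reading of the term | AE? | Follow-up after Visit 8 |
|---|---|---|
| Includes LSRs | No | None |
| PLA, SSA and dimensions only | Yes, if clinically relevant | Yes, if judged related |

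The same finding can be classified in opposite ways by two sites that both follow the text.

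**5. What is still captured.** All eleven signs are graded through Day 106 and tabulated under Section 9.2. What is lost on the first reading is the AE entry and the course after Visit 8.

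**The case against.** The strongest reply is that the term is undefined and the narrower reading is available. On that reading the general sentence governs scars and pigment change, and the existing follow-up applies. This stands to the extent that the text does not compel the exclusion. It does not remove the problem: the inclusive reading is the more natural one given the Synopsis and Section 5.3, and two adjacent sentences giving opposite answers need reconciling either way.

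A second reply is that serious reactions are covered. Section 7.1.2 includes persistent or significant disability and important medical events, and Section 7.2.2 follows SAEs past the last visit. This also stands and limits the point to non-serious reactions, but an untreated cosmetic scar or pigment change would not ordinarily qualify as serious.

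A third is that the signs are graded and tabulated anyway, with no inferential safety testing planned. That is right as far as Day 106. It supplies neither an AE record nor an outcome after discharge.

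A reader might infer more than the documents support:

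- *That the trial cannot tell transient from lasting change.* Repeated grading to Day 106 shows which signs resolve by then and which persist. Only the later course is missing.
- *That the rule works against vehicle and active groups unequally, because cleared lesions lose the second application.* Between Visits 2 and 4 PLA is not assessed. Retreatment is decided at Visit 4 in every group, and afterwards no group has an application pending. The clear rates in Section 9.3 (at least 0.325 against about 0.031) refer to Visit 8. No Visit 4 rate is given.
- *That 84/105 = 80% measures missed events.* It is the share of nominal follow-up days on which one of two triggers is unavailable in retreated subjects. The other trigger stays open throughout.

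**Conclusion.** The point holds in a limited form. If *target lesion assessments* includes LSRs, then from Visit 4 to Visit 8 (84 days nominally, 76 to 92 with the windows) an ulceration, atrophy, scar or pigment change that is non-serious and needs no therapy is not an AE. If still present at Visit 8, it has no required follow-up. The loss is confined to AE incidence and to outcome after Visit 8. The reactions are not missing from the safety data to Day 106.

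The conclusion rests on the inclusive reading of an undefined term. Under the narrower reading the exclusion disappears and the defect is an ambiguity that sites may resolve differently. The number of subjects affected cannot be estimated, since the documents give no rate of residual signs or of their treatment. Because these are the harms the introduction singles out, and the correction is small, Section 7.1.1 should be amended.

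**What to change.** Amend the paragraph in Section 7.1.1 to do three things:

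1. Reconcile the general sentence with the restriction that follows it.
2. Define *target lesion assessments* as PLA, SSA and lesion dimensions, and state that transient LSRs stay in the LSR tables, so that the narrower definition does not turn every passing reaction into an AE.
3. State that ulceration, atrophy, scarring, hypo-pigmentation or hyper-pigmentation above the Visit 2 pre-application grade and still present at the subject's last visit is recorded as an AE whether or not therapy is given.

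Such a finding falls within the reporting period in Section 7.1.4, which runs to the end of the last visit. The existing follow-up in Section 7.2.1 then applies unchanged to those judged related. The baseline and final grades are already collected, so no new visit, scale or scheduled assessment is needed.

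The cost is some extra AE entries, a less favourable AE rate, and follow-up beyond Visit 8 of subjects whose residual signs are judged related.
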